#### AIM 1. Describe PLWH initiating CAB+RPV LA regimen

Baseline characteristics including demographics, clinical, immunological and virological characteristics at baseline (i.e. at initiation of regimen) will be described using the following descriptive statistics: n (non-missing sample size), median, 1st quartile, and 3rd quartile. The frequency and percentages (based on the non-missing sample size) of observed levels will be reported for all categorical variables.

# AIM 2. Assess adherence, durability and discontinuation for PLWH starting CAB+RPV LA regimen

The proportion of study participants discontinuing the regimen will be assessed at 6, 12-and 24-months using the Kaplan-Meier method. The two-sided 95% confidence intervals of the proportions will be calculated with Kalbfleisch and Prentice's formula. Time to event will be defined as the time between the date of the initiation of CAB+RPV LA regimen and the date of discontinuation of CAB+RPV LA regimen. Death, cause of death where available and lost to follow-up will be excluded from this analysis but will be tabulated and reported separately. Follow-up will be censored at the analysis time point. The estimated median time to discontinuation will be calculated with the two-sided 95% associated confidence interval. Reasons for discontinuation will be given and frequencies and percentages will be reported. Number of individuals that experience blips  $\geq$ 50 to <200 copies/mL will be tabulated along with the number of individuals that have CVF and remain on regimen. Kaplan Meier curves will be plotted with the number of participants at risk at baseline, 6, 12, and 24-month.

The number and proportion and the two-sided 95% associated confidence interval of participants that missed one or more consecutive injections without taking daily oral bridging therapy or any other oral ARV regimen while not on CAB+RPV LA regimen will be calculated. The proportion will be estimated by the number of individuals who missed one or more consecutive injections divided by the total number of study participants in the analysis. The mean and median number of injections missed during a 12-month period will be described by median, 1st quartile, and 3rd quartile.

The number and proportion and the two-sided 95% confidence interval of proportion of individuals who received the injections seven or more days later than their scheduled

injection visit will be calculated. The proportion will be estimated by the number of individuals who received the injections seven or more days later than their scheduled injection visit divided by the total number of study participants in the analysis. The duration of delayed injections will be described by median, 1st quartile, and 3rd quartile.

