#### 8.3.2. Outcome definitions

**Table 1.** Regimen discontinuation: Reasons for discontinuation as tabulated below will be collected for all participants switching off CAB+RPV LA regimen.

Code	Reason for Stopping Treatment
1	Treatment failure (i.e. virological, immunological, and/or clinical failure
1.1	Virological failure
1.2	Partial virological failure (multiple blips, low level viraemia)
1.3	Immunological failure - CD4 drop (25% or more)
1.4	Clinical progression
1.5	Resistance (based on test result)
2	Abnormal fat redistribution
3	Concern of cardiovascular disease
3.1	Dyslipidaemia
3.2	Cardiovascular disease
3.3	Weight gain
4	Hypersensitivity reaction (skin eruption etc.)
5	Toxicity, predominantly from abdomen/G-I tract
5.1	Toxicity - Liver
5.2	Toxicity - Pancreas
6	Toxicity, predominantly from nervous system
6.1	Toxicity - peripheral neuropathy
6.2	Toxicity - neuropsychiatric

6.3	Toxicity - headache
7	Toxicity, predominantly from kidneys
8	Toxicity, predominantly from endocrine system
8.1	Diabetes
9	Haematological toxicity (anemia etc.)
10	Hyperlactataemia/lactic acidosis
11	Bone toxicity
12	Social contra-indication
13	Contra-indication unspecified
14	Pregnancy - toxicity concerns (during pregnancy)
15	Pregnancy - switch to a more appropriate regimen for PMTCT
16	Death
17	Toxicity, unspecified
	Availability of more effective treatment (not specifically failure or side effect
18	related)
18.1	Simplified treatment available
18.2	Treatment too complex
19	Drug interaction
19.1	Drug interaction - commencing TB/BCG treatment
20	Injection fatigue (not related to safety)
21	Injection Site Reaction
22	Non-adherence
23	Drug not available
24	Other causes, not specified above
25	Lost to follow-up
26	Defaulter
27	Individual's wish/decision, not specified above
28	Physician decision to discontinue due to confirmed low level viremia (50-200)
29	Physician's decision, not specified above
99	Unknown

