### 8.4. Study size

The study will aim to enroll 1000 PLWH with VL <50 copies/mL, without present or past evidence of viral resistance to, and no prior virological failure with agents of the NNRTI and INI class initiating CAB+RPV LA regimen.

There is no formal statistical hypothesis to be tested in these analyses. The study will focus on absolute effectiveness estimation. Confidence intervals, constructed using the exact Clopper-Pearson method based on the cumulative probabilities of the binomial distribution, are presented in Table 2, 3, 4 and are designed to give estimates of precision.

It is anticipated that data from 1000 participants are thought adequate to meet the study objectives. In the ATLAS study in which participants switched from their PI, NNRTI, or INSTI based oral triple therapy regimen to CAB+RPV LA regimen, the percentage of participants with virologic failure (2 confirmed HIV RNA  $\geq$ 50 copies/mL) and treatment discontinuation were, respectively, 1.6% (95% CI 0.5 to 3.4) and 8.4% (95% CI 5.6 to 12.1) at week 48. Among the 3 individuals with confirmed virological failure, all selected drug resistance mutations. For resistance, we assume a 50% resistance rate at month-24 among those with virological failure.

With 1000 individuals, the precision for the estimation of virologic failure rate will range between 0.9 and 1.5% for a failure rate ranging from 2 to 6% as shown below in Table 2.

Confidence Level	Sample Size (N)	CI Width	Virologic Failure (P)	Lower Limit	Upper Limit
0.95	1000	0.019	0.02	0.012	0.031
0.95	1000	0.023	0.03	0.020	0.043
0.95	1000	0.025	0.04	0.029	0.054
0.95	1000	0.028	0.05	0.037	0.065
0.95	1000	0.031	0.06	0.046	0.077

The corresponding precision for the discontinuation rate will range between 1.7 to 2.3 for a rate ranging from 8 to 16% as shown below in Table 3.

Confidence Level	Sample Size (N)	CI Width	Discontinuation (P)	Lower Limit	Upper Limit
0.95	1000	0.035	0.08	0.064	0.099
0.95	1000	0.038	0.10	0.082	0.120
0.95	1000	0.041	0.12	0.101	0.142
0.95	1000	0.044	0.14	0.119	0.163
0.95	1000	0.046	0.16	0.138	0.184

If the virological failure rate is ranging from 2 to 6%, then the number of participants to be tested for genotypic resistance will range from 20 to 60 individuals. With these numbers of subjects, the precision for the estimation of resistance rate will range from 12.7% (with 60 individuals) to 21.9% (with 20 individuals) for resistance rate of 50%, as shown below in table 4.

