#### 8.7. Data analysis

All enrolled participants who receive at least one dose of the CAB+RPV LA regimen will be included in the analysis. Participants who are prescribed but never receive a dose of CAB+RPV LA regimen will be excluded from the analysis. Study results will be stratified by the regimen used (Q4/Monthly dosing vs Q8/Every 2 month dosing). Further, study results for co-infected patients with hepatitis B or C will be presented separately. All continuous variables will be summarized using the following descriptive statistics: n (non-missing sample size), mean, standard deviation, 1st quartile, median, 3rd quartile, maximum and minimum. The frequency and percentages (based on the non-missing sample size) of observed levels will be reported for all categorical variables. Data will be analyzed using SAS®, SPSS® or STATA®.

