# AIM 3. Assess the clinical effectiveness among PLWH who initiate CAB+RPV LA regimen

Given that this study involves PLWH in routine clinical care, and who may not attend clinic appointments at 6, 12 or 24 months, a window of 12 weeks around the date in question will be used for virologic failure. Thus, the proportion with virologic failure during first six months, at 6, 12 or 24 months  $\pm$  6 weeks will be used; and if none is available, the first measurement during first six months, after 6, 12 or 24 months (and at most 6 weeks after the measurement).

Proportion of participants who continue to be suppressed (VL of <50 copies/mL) at each time point (after 6, 12 and 24 months of follow up) will be estimated, as well as proportion of individuals with VL of <200 copies/mL. CD4 counts will also be assessed. The proportion of participants with virologic failure (2 consecutive HIV RNA VL  $\geq$ 200 copies/mL or one HIV RNA VL level  $\geq$ 200 copies/mL followed by a discontinuation of CAB+RPV LA regimen) will be estimated and time to failure will be assessed by the Kaplan-Meier method. The two-sided 95% associated confidence interval will be calculated with Kalbfleisch and Prentice's formula. Time to event will be defined as the time between the date of the initiation of CAB+RPV LA regimen and the date of virologic failure. Follow-up will be censored at the analysis time point, or the date of last study contact, or date of discontinuation of CAB+RPV LA regimen, or the date of lost to follow-up, whichever will occur first.

Genotypic resistance testing will be performed in participants with confirmed HIV RNA VL  $\geq$ 200 copies/mL. Resistance interpretation will be given using the Stanford algorithm (https://hivdb.stanford.edu/hivdb/by-mutations). All drug resistance mutations identified will be described and number and percentage indicated. The proportion of participants with genotypic resistance viruses among those with virological failure will be estimated by the number of participants with genotypic resistance viruses divided by the total number of participants with virological failure. The associated two-sided 95% exact (Clopper–Pearson) confidence intervals will be calculated. The frequency of viral subtype among those with virologic failure will be reported.

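### The Aim 2 discontinuation analysis excludes deaths and losses to follow-up instead of censoring them, which conflicts with Section 8.7, Aim 3 and Table 1 and can bias the estimate in either direction

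*Protocol*

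**What the plan says.** Section 8.7, Aim 2 gives the estimator: "The proportion of study participants discontinuing the regimen will be assessed at 6, 12-and 24-months using the Kaplan-Meier method". Time runs from initiation of the regimen to its discontinuation. On incomplete follow-up it says that death, its cause where known, and "lost to follow-up will be excluded from this analysis but will be tabulated and reported separately". The one censoring rule comes next: "Follow-up will be censored at the analysis time point. The estimated median time to discontinuation".

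Three other places bear on this.

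- The opening of Section 8.7 sets the analysis population: "All enrolled participants who receive at least one dose of the CAB+RPV LA regimen will be included in the analysis".
- Aim 3 (virologic failure) lists its censoring dates: the analysis time point, last study contact, discontinuation, "or the date of lost to follow-up, whichever will occur first".
- Section 8.3.2, Table 1 is introduced with "Reasons for discontinuation as tabulated below will be collected for all participants switching off CAB+RPV LA regimen". Its codes include 16 (death), 25 (lost to follow-up) and 26 (defaulter). The case report form in Annex 1 offers the same three as reasons for discontinuation, next to a discontinuation date. Aim 2 does not mention defaulters.

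**The concern.** Kaplan-Meier deals with incomplete follow-up by keeping people at risk until they leave and then censoring them. Removing them altogether because they later die or are lost discards the event-free time they contributed and conditions the estimate on the future. A participant coded 25 is also treated in two ways: the case report form can give that person a discontinuation date, which meets Aim 2's event definition, and the next rule in Aim 2 takes the person out. Because default is not addressed, a site's choice between codes 25 and 26 could decide whether someone is an event or is missing from the curve.

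Discontinuation and durability are Objective 2 of a joint PASS/PAES, and the planned Cox model for discontinuation uses the same outcome. The effect on that model was not calculated.

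**Working it through.** **The plan's own figure.** Section 8.4 states: "The corresponding precision for the discontinuation rate will range between 1.7 to 2.3 for a rate ranging from 8 to 16" percent. Exact Clopper-Pearson limits with N = 1000 reproduce all five rows of Table 3: 0.0639–0.0986 at 8%, 0.0821–0.1203 at 10%, 0.1005–0.1418 at 12%, 0.1191–0.1631 at 14% and 0.1378–0.1842 at 16%. Half-widths run from 1.73 to 2.32 points, and the half-width is 2.06 at 12%. Table 3 is correct as printed.

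**Inputs.** From the protocol: N = 1000, 24 months on regimen, planned discontinuation rates of 8% to 16%. Assumed, because the protocol gives no rate: a net probability L of loss or death by month 24 of 5% to 20%, constant hazards, and loss independent of stopping.

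**Formulas.** Let D be the true 24-month discontinuation, a = −ln(1−D) and b = −ln(1−L).

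- Still on regimen and in follow-up: S = exp(−(a+b)) = (1−D)(1−L).
- Observed to discontinue: F = a/(a+b) × (1−S).
- Censored at loss: D.
- Excluded if lost or dead before discontinuing: F/(F+S).
- Carried to month 24 as still on regimen: F.
- Loss and death counted as events: 1−S.

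**Worked case, D = 12%, L = 10%.** a = 0.1278 and b = 0.1054. S = 0.88 × 0.90 = 0.792. F = 0.1278/0.2332 × 0.208 = 0.1140. Excluded: 0.1140/(0.1140 + 0.792) = 0.1258. Counted as events: 1 − 0.792 = 0.208.

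| D = 12% | L = 5% | L = 10% | L = 20% |
|---|---|---|---|
| Carried as on regimen | 11.7% | 11.4% | 10.8% |
| Censored | 12.0% | 12.0% | 12.0% |
| Excluded | 12.3% | 12.6% | 13.3% |
| Counted as events | 16.4% | 20.8% | 29.6% |

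Over the wider grid, exclusion exceeds censoring by 0.2 points (D = 8%, L = 5%: 8.2% against 8.0%) up to 1.6 points (D = 16%, L = 20%: 17.6% against 16.0%).

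**When the direction changes (D = 12%, L = 10%).**

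- Suppose people lost after discontinuing are removed too. The excess vanishes if their loss hazard equals that before stopping (12.0%), and it reverses if that hazard is doubled (11.4%).
- Suppose a share q of the loss hazard is really stopping. The true figure is 1 − 0.88 × 0.90^q: 12.5% at q = 5%, 12.9% at q = 10% and 16.5% at q = 50%. Exclusion returns 12.6% throughout, so it understates from somewhere between q = 5% and q = 10% upward.

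**Earlier time points (D = 12%, L = 20%).** The censored six-month figure is 1 − exp(−0.1278/4) = 3.1%. Removing everyone lost or dead by month 24 gives 0.0306/0.8118 = 3.8%. Because the annual interim reports are cumulative, later losses would change time points already reported.

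**The case against.** The strongest reply is that the sentence concerns events, not people. Its subject includes a cause of death, which is not a participant, so it may mean only that death and loss do not count as discontinuations. That would fit the all-dosed population, and Section 7 also names discontinuation and loss to follow-up as separate things. Table 1 is a list of reasons to collect, and Aim 2 can decide which of them are events. Exact censoring dates are often left to a statistical analysis plan.

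Part of this stands: the milder reading is open. It does not rescue the text. Section 8.7 uses the same verb for participants who were never dosed, where it can only mean removal, and Aim 3 shows that censoring at loss is written out where it is intended. Under the milder reading, the one stated rule would carry lost participants as still on regimen to the time point, which is also biased (11.4% or 10.8% against 12.0%). The sentence is a stated rule, so it is not a detail left for later.

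Two stronger inferences should be resisted. A reader might infer that the rule overstates discontinuation in general. The upward shift needs non-informative loss and removal limited to people lost before discontinuing; otherwise it can vanish or reverse. A reader might also infer that the Table 3 precision is not delivered. Table 3 reproduces. With 20% loss about 812 of 1000 would remain, and the half-width at 12% would be about 2.3 instead of 2.1 points; censoring also costs information.

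**Conclusion.** The Aim 2 rule is wrong if read literally and incomplete if read mildly, and it disagrees with the analysis population, the Aim 3 censoring rule and the discontinuation codes. At 12% true discontinuation and an assumed 5% to 20% non-informative loss or death, exclusion adds 0.3 to 1.3 points, within the 2.06-point half-width. Carrying losses forward subtracts 0.3 to 1.2 points. The larger uncertainty is the coding: counting loss and death as events gives 16.4% to 29.6%, far outside that half-width.

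The loss rates, constant hazards and independence are assumptions, so the sizes are illustrative. That the passages conflict does not depend on them. Default is a separate gap: Aim 2 neither excludes code 26 nor says whether it is an event.

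**What to change.** In Section 8.7, Aim 2, replace the exclusion with a rule that:

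- keeps every dosed participant in the risk set;
- censors loss to follow-up at the last date known on regimen;
- treats death as a competing event, with a cumulative incidence estimate, or censors it at the date of death;
- states whether code 26 is an event.

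Align Table 1, the Annex 1 reason list, the population statement and the Aim 3 censoring text with that rule, and say that codes 16 and 25 are not events in the main estimate. Add a sensitivity analysis counting codes 25 and 26 as discontinuation.

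The cost is a few lines of wording and one extra analysis. No new data are needed. The End of Study form holds the withdrawal date and reason, including death and loss, and the regimen form holds actual injection dates and the discontinuation date. Since the End of Study form has a single completion or withdrawal date, the rule should name which recorded date defines the last date known on regimen.

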#### **2.** Clinical effectiveness: assessed using the following measures:

- 1. Proportion of individuals, virologically suppressed/undetectable (<50 copies/mL) at 6,12 and 24 months following initiation of CAB+RPV LA regimen
- 2. Proportion of individuals with VL of  $<\!200$  copies/mL at 6,12 and 24 months following initiation of CAB+RPV LA regimen
- 3. Proportion of individuals with confirmed virologic failure (CVF) during the first 6 months, and at 6,12 and 24 months following initiation of CAB+RPV LA regimen defined as

- Two consecutive HIV RNA VL levels ≥200 copies/mL or
- One HIV RNA VL level \ge 200 copies/mL and regimen discontinuation within 4 months of VL \ge 200 copies/mL
- **3.** Resistance Testing: This is a non-interventional study aiming to capture SoC for PLWH in real world setting. Testing for resistance and subtype at virologic failure is part of SoC and the study will include only the clinical sites that follow the guidance for resistance testing.
  - Resistance testing along with subtype will be done for all participants with virologic failure during the 24 month follow-up period while on CAB+RPV LA
  - Resistance testing along with subtype will also be done during the 48 months following any switch from CAB+RPV LA in all participants with subsequent virologic failure on their new regimen(s) during the follow up period

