#### eForm Code: HIVRNA eForm Title: HIV RNA Viral Load - Annotations Table

ID	CODE	NAME	EXP.CODE	TYPE	FMT/LEN	DERIVATION	CAT. VALUES		
1	20R1ID D	Subject ID	20R1ID D	Text	10	R2F:DEMOG:20R3ID			
Repea	epeating Question Group: , Borders: Yes, RowStatus: Yes, RowNumbers: Yes, DisplayRows: 3, InitialRows: 1, Min Repeats: 1, Max Repeats: 20, Main Row Type: Single-Line, Sub Row Type: Multi-Line								
2	VLDA I	Date of sample	VLDA I	Date/Time	aa/mm/yyyy				
3	VLGL	Viral Load Equal To, Greater Tha or Less Than	1VLGL	Category	1, Optional		0=< 1=> 2==		
4	VLOAD	HIV RNA viral load	VLOAD	Integer	#####9				
5	VLVF	Assessed as Virological Failure	VLVF	Category	3		N=No Y=Yes		
6	VLRET	Was a retest carried out?	VLRET	Category	3		N=No Y=Yes		
7	Hotlink			Hotlink		BSL:RESTST			
Repea			,	,		, Max Repeats: 20, Main Row Type: Single-Line, Sub Row Type: Multi-Line			
8	CRREAS	Data Review Reason	CRREAS	Category	36, Optional		See Appendix		
9	CRDAT		CRDAT		dd/mm/yyyy, Optional				
10	CRINOT	Notes for Next Review	CRNO I	Text	500, Optional				

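### A last viral load of 200 or more with no later value is censored as event-free, so the failure estimate can only be unaffected or too low, and the protocol's rules on loss after such a value conflict

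*Protocol*

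**What the plan says.** Protocol section 8.3.2 (clinical effectiveness) gives CVF two arms. The first needs "Two consecutive HIV RNA VL levels" at or above 200 copies/mL, with no maximum interval between the two samples. The second needs one such value "and regimen discontinuation within 4 months of VL" at that level.

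Section 8.7, AIM 3, restates the second arm without the time limit, as one value of at least 200 "copies/mL followed by a discontinuation of CAB+RPV LA regimen) will be estimated and time to failure will be assessed by the Kaplan-Meier method". Its censoring rule is: "Follow-up will be censored at the analysis time point, or the date of last study contact". Discontinuation and loss to follow-up are further censoring dates, and the earliest applies.

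Section 8.7, AIM 2, supplies the only other categories for raised values. "Number of individuals that experience blips" of 50 to below 200 copies/mL "will be tabulated along with the number of individuals that have CVF and remain on regimen".

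Table 1 in section 8.3.2 lists loss to follow-up (code 25) and defaulter (code 26) among the reasons for stopping the regimen, and the case report form in Annex 1 repeats both. The viral load form in Annex 1 also asks, for each sample, "Was a retest carried out".

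**The concern.** A single VL of 200 or more on a regimen not recorded as stopped is too high to be a blip and does not meet either arm of CVF. If a later value exists, it either completes the pair or shows re-suppression. If none exists, because the person was lost, stopped attending or reached the data cut, the case stays open and AIM 3 closes it as a censored, event-free observation.

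Kaplan-Meier estimation assumes that people censored have the same later risk as those still followed. That is doubtful when the last known fact is viraemia and the reason for censoring is loss or non-attendance. The study adds no visits to routine care (section 8.2.3), AIM 3 expects missed appointments, and section 6.2 links missed dosing visits to viral rebound. Those who miss the confirming sample may well be those who are failing.

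At stake is the headline failure proportion, planned at 2% to 6%, where a handful of people matters.

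**Working it through.** **Planned precision, reproduced.** Exact Clopper-Pearson limits for 20 of 1000 are 1.23% and 3.07%, half-width 0.92 points. For 60 of 1000 they are 4.61% and 7.66%, half-width 1.52 points. Both agree with Table 2 in section 8.4 (precision 0.9 to 1.5%).

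**Where a terminal VL of 200 or more lands.**

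| Rule | Result |
|---|---|
| Blip, 50 to below 200 (AIM 2) | No, too high |
| CVF arm 1, two consecutive values (8.3.2) | No, no second value |
| CVF arm 2, one value plus discontinuation (8.3.2) | No, unless loss counts as discontinuation |
| CVF and still on regimen (AIM 2) | No, not CVF |
| Time to failure (AIM 3) | Censored, no event |

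**Do the landmark measures catch it?** The proportions below 50 and below 200 copies/mL are reported at 6, 12 and 24 months, with windows of ±6 weeks. Between the 12- and 24-month windows lie about 52 − 6 − 6 = 40 weeks. A person with a high value there who is then lost has no 24-month value. Section 8.7 bases percentages on the non-missing sample, so on that rule the person also leaves the 24-month denominators.

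**Where the sections conflict.**
- VL of 200 or more, then loss within 4 months: CVF under section 8.3.2 if codes 25 and 26 are discontinuations, but AIM 3 censors at loss. AIM 2 also leaves loss out of the discontinuation analysis, which points the other way from Table 1.
- A single VL of 200 or more, then discontinuation at month 5: failure under AIM 3, not under section 8.3.2.

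**Size.** Let u be the unresolved participants per 1000 and q the share who are true failures. The documents give neither, so both are assumptions. With 20 confirmed failures the proportion is (20 + u × q)/1000.

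| u | q = 0 | q = 0.5 | q = 1 |
|---|---|---|---|
| 5 | 2.0% | 2.25% | 2.5% |
| 10 | 2.0% | 2.5% | 3.0% |
| 15 | 2.0% | 2.75% | 3.5% |

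Ten unresolved cases, all true failures, move the estimate by 1.0 point, about the planned half-width. If none are true failures the shift is zero. With 60 confirmed failures, 5 to 15 cases with q = 1 give 6.5% to 7.5%.

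**Kaplan-Meier check.** A simulation with 20 failures and an assumed 160 other censorings among 1000 gave 24-month failure of 2.2%, whether the unresolved cases stayed at risk to month 24 or were censored at the high value. Counting 5 or 10 of them as events gave 2.7% or 3.3%.

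**The case against.** The strongest reply is that requiring confirmation is a deliberate, stated choice. The study used for planning in section 8.4 also reports a confirmed definition, and extra sensitivity analyses are commonly left to the statistical analysis plan, which is not at hand. It stands that the main definition needs no change. But the protocol itself fixes the definition, the tabulated categories and the censoring rule, and its sections disagree, so the point is not only one of missing detail.

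The exposed group is also small. Because the two values need only be consecutive, any later routine sample settles the case, and cumulative annual reports can resolve values left open at an interim cut. A high value close to month 24 normally falls in that window and shows on the below-200 measure. All of this stands, and it confines the problem to terminal values.

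Loss may already count as failure through codes 25 and 26. That reading is open, but AIM 3 censors at loss, so the document does not settle it.

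A reader might infer three stronger things that the documents do not support:
- *Such people are scored as successes.* Censoring is not success, and a high value used in a landmark window is a non-success on both suppression measures.
- *The failure rate is biased low.* That needs some unresolved cases to be true failures. The documents show only that any error cannot go upward.
- *Isolated high values that re-suppress are missed failures.* They are unconfirmed rises. A table row for them is a reporting preference.

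**Conclusion.** The point holds in a limited form. A terminal, unconfirmed VL of 200 or more with no recorded stop has no category and is censored event-free. Where loss or missed visits lie behind it, the censoring is plausibly informative and the failure proportion can only be unaffected or too low. The landmark measures do not reliably catch these people. Separately, the protocol is inconsistent on whether loss after such a value is an event or a censoring, and on the 4-month limit.

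The size is not known. The span from 2.0% to 3.5% rests on 20 confirmed failures per 1000, an assumed 5 to 15 unresolved cases, and a true-failure share anywhere from none to all. The upper end exceeds the planned half-width of 0.92 points, and the lower end is no effect at all. That supports bounding the estimate. It does not show that the estimate is wrong.

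**What to change.** - Keep the main CVF definition.
- Reconcile Table 1 and the CVF definition in section 8.3.2 with AIM 3 in section 8.7: state whether loss after a VL of 200 or more is a discontinuation event or a censoring, and whether the 4-month limit applies.
- Report the number of participants whose last available on-regimen VL is 200 or more and unconfirmed.
- Prespecify one sensitivity analysis that counts them as failures on the date of that VL, labelled as an upper bound.

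Sample dates, values and the retest field are already collected in Annex 1, so no new data are needed. The cost is one more analysis and one reported count. The sensitivity estimate will be the same or less favourable, and it may count some transient rises as failures, which is why it should be presented as a bound beside the main result.
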